11.8.2. Meta-Analysis Post-Regulatory Approval

To meet US regulatory requirements post-approval (refer to Section 1.2, Overall Rationale and Goals for the Study), results from this study will be exported and integrated with results from CANVAS-R to demonstrate that the upper bound of the 95% CI around the HR for important CV events (MACE) is <1.3. The primary objective of the CANVAS-R study is to evaluate the effects of canagliflozin relative to placebo on albuminuria progression. The CANVAS and CANVAS-R studies will share similar inclusion and exclusion criteria and will enroll similar patient populations. Both studies will require a standardized collection and evaluation of MACE endpoint events by the same Endpoint Adjudication Committee (see Section 9.3.5).

A CV meta-analysis was conducted with 201 MACE plus events. The pre-approval condition was met by demonstrating that the upper bound of the 2-sided 95% CI for the HR was <1.8. The post-approval condition for the exclusion of HR of 1.3 was then tested with 0.001 alpha, and was not met.

As part of the post-approval CV safety requirement, a meta-analysis based on the data from this study and the data from another large-scale study, CANVAS-R, will be conducted when at least 688 MACE events are accumulated in the 2 studies, which is

projected to occur prior to April 2017. With at least 688 MACE events, the power to show the HR <1.3 is about 90% with a 2-sided significance level of 0.05.

The ‘Statistical Analysis Plan for the Post-Marketing Requirement for the CV Risk Assessment of Canagliflozin (CANVAS and CANVAS-R)’ was finalized and submitted to FDA.

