Increases in low-density lipoprotein cholesterol (LDL-C) were observed with canagliflozin: in a pooled analysis of placebo-controlled 26-week studies, increases in LDL-C relative to placebo were 4.4 mg/dL (0.11 mmol/L) and 8.2 mg/dL (0.21 mmol/L) at the 100 mg and 300 mg doses, respectively. Relative increases in Apo B, non-HDL-C, and LDL particle number were approximately half as large as the rise in LDL-C. The changes in the CV risk profile with canagliflozin include reductions in SBP and increases in LDL-C, both established CV risk factors, and validated as surrogate endpoints. Improvements in other endpoints associated with CV risk, but not established as surrogate endpoints for CV benefit, such as body weight, glycemic control, HDL-C, and TG were also observed with canagliflozin. The cross-program CV meta-analysis (including results from the dedicated CV safety study) observed a hazard ratio (HR) of 0.91 for a pre-specified composite endpoint of CV death, non-fatal MI, non-fatal stroke, and hospitalized unstable angina (95% confidence interval [CI]: 0.68, 1.22), showing no signal for an increase in the CV risk.

As of 11 May 2015, in the T2DM clinical development program, incidence rates of unblinded serious adverse events of DKA, ketoacidosis, metabolic acidosis, and acidosis were 0.0522 (0.07%, 4/5337), 0.0763 (0.11%, 6/5350), and 0.0238 (0.03%, 2/6909) per 100 subject-years with canagliflozin 100 mg, canagliflozin 300 mg, and comparator, respectively. Of the 12 subjects with serious adverse events of DKA, ketoacidosis, metabolic acidosis, or acidosis (all of whom were hospitalized), 6 subjects on

canagliflozin (3 on canagliflozin 100 mg and 3 on canagliflozin 300 mg), and none on comparator were reported to have autoimmune diabetes (latent autoimmune diabetes of adulthood [LADA] or type 1 diabetes) or tested positive for GAD65 antibodies after being diagnosed with a serious DKA-related event. Eight of the 10 subjects on canagliflozin were receiving insulin therapy. The blood glucose values around the time of admission in 9 of 10 subjects on canagliflozin ranged from 347 to 571 mg/dL (9.3 to 31.7 mmol/L). The remaining subject had blood glucose values ranging from 148 to 320 mg/dL (8.2 to 17.8 mmol/L). Diabetic ketoacidosis has also been reported during post-marketing surveillance and has occurred in patients with blood glucose values less than 250 mg/dL (13.9 mmol/L). As a result, DKA is considered a rare adverse drug reaction.

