The study was modified (as of amendment INT-5) because the cross-program meta-analysis of the pre-approval CV safety endpoint was unblinded to the sponsor to prepare regulatory submissions (originally this was to be unblinded to the study IDMC only); this was done based upon a decision by the sponsor, so that the impact of the small dose-related increase in LDL-C observed with canagliflozin treatment in Phase 3 program on the CV HR could be evaluated. Due to the unblinding of these CV endpoint results, the study Steering Committee noted that the addition to the CANVAS study of the planned second cohort of subjects would not provide a robust assessment of the primary CV protection hypothesis.

As part of the safety and tolerability objective, the study was originally designed to be able to show, within 4 years of marketing approval in the US, that the upper bound of the CV HR for MACE plus unstable angina events was <1.3. Upon approval of canagliflozin for marketing, the US FDA required that the 1.3 requirement be met with MACE events (ie, CV death, nonfatal MI, and nonfatal stroke, and excluding hospitalized unstable angina), and that additional subjects with high CV risk be recruited to explore events occurring within the first 30 days after initiation of therapy. Accordingly, it was not possible to fulfill these requirements solely with the ongoing CANVAS study within the 4 year post-approval timeframe required by FDA, and therefore another large-scale study of the effects of canagliflozin compared to placebo (CANVAS-R; 28431754DIA4003) with 5,700 subjects is being initiated to meet the FDA CV safety requirement.

The primary objective of the CANVAS-R study is to evaluate the effects of canagliflozin relative to placebo on albuminuria progression. The CANVAS and CANVAS-R studies will share similar inclusion and exclusion criteria and will enroll similar patient

populations. Both studies will require a standardized collection and evaluation of MACE endpoint events by the same Endpoint Adjudication Committee (see Section 9.3.5).

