11.3. Sample Size Determination

The sample size for the recruitment of the initial 4,500 subjects was based upon having a sufficient number of participants to support, in concert with the other controlled clinical trials in the canagliflozin development program, a detailed pre-approval assessment of the safety and tolerability of canagliflozin. Data from this initial cohort were exported and integrated with data from other Phase 3 well-controlled studies to support a planned pre-approval meta-analysis to demonstrate that the upper bound of the 2-sided 95% CI for the CV HR of canagliflozin relative to control in composite endpoint events (MACE and hospitalized unstable angina) was <1.8 ; the current US regulatory requirements for filing. The FDA post-marketing requirements for canagliflozin demand a subsequent estimate of CV safety that will be performed on data from CANVAS and CANVAS-R, when sufficient events have occurred to demonstrate that the upper bound of the 95% CI HR is <1.3 based on MACE (excluding hospitalized unstable angina).

The assumed per annum event rate is 2.25% and the per annum dropout rate is 5%. With an enrollment period 1.5 years, 4,500 randomized subjects were projected to contribute sufficient CV events to support the pre-approval CV meta-analysis.

The original phased recruitment strategy allowed for an interim assessment of study feasibility to demonstrate the primary hypothesis of CV benefit using the results of the interim analysis. Results from the interim analysis (conducted after approximately 2 to

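### Should the final test of the HR 1.3 condition give up the 0.001 alpha already used in the pre-approval meta-analysis?

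*Protocol*

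**What the plan says.** Section 11.8.2 gives two levels for excluding an HR of 1.3.

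- **Earlier test.** "A CV meta-analysis was conducted with 201 MACE plus events". The pre-approval margin of 1.8 was excluded, after which "The post-approval condition for the exclusion of HR of 1.3 was then tested with 0.001 alpha, and was not met". The section does not say whether the 0.001 is one-sided or two-sided.
- **Final test.** Results from CANVAS and CANVAS-R are to be combined to "demonstrate that the upper bound of the 95% CI around the HR for important CV events (MACE) is <1.3". On size, "With at least 688 MACE events, the power to show the HR <1.3 is about 90% with a 2-sided significance level of 0.05".

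Section 1.2 links the two. The 1.3 bound was first planned on MACE plus unstable angina, and on approval "the US FDA required that the 1.3 requirement be met with MACE events", with further high-risk subjects to be recruited. Section 1.1.2 reports that the cross-program meta-analysis "observed a hazard ratio (HR) of 0.91 for a pre-specified composite endpoint" (95% CI 0.68 to 1.22). Section 11.8.2 adds that a separate SAP for the post-marketing CV assessment was finalized and submitted to FDA.

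**The concern.** The protocol itself calls the 201-event analysis a test of the post-approval condition, and section 1.2 speaks of the same 1.3 requirement carried over to a narrower endpoint. CANVAS data enter both analyses. On that reading one null hypothesis is tested twice, first at 0.001 and then at the full 0.05, and the levels sum to 0.051. A level as small as 0.001 is normally chosen to save alpha for a later test, so a reader expects the remainder (0.049) to appear as the final level. It does not, and nothing says that no deduction is meant.

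This is the regulatory decision test for cardiovascular safety, and sponsor personnel had seen the first result. If the final bound fell very close to 1.3, the unspent or double-counted 0.001 could be questioned.

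**Working it through.** **Inputs.** Events 201 and 688, levels 0.001 and 0.05, and margin 1.3 (section 11.8.2); HR 0.91, 95% CI 0.68 to 1.22 (section 1.1.2); doses combined against placebo after 1:1:1 allocation, so 2:1 in CANVAS (section 11.2); about 400 of the events expected in CANVAS (section 11.3). Assumptions: true HR 1.0 for power; CANVAS-R allocation is not given and is taken as 2:1, with 1:1 as the alternative.

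**1. The plan's power.** Power = Φ(ln 1.3 × √(688 × 2/9) − 1.960) = Φ(0.2624 × 12.365 − 1.960) = Φ(1.284) = 90.05%. This reproduces the stated figure of about 90%. With 400 events at 2:1 and 288 at 1:1 it is 91.4%. The plan's arithmetic is sound and uses the full 0.05.

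**2. The earlier result.** SE = (ln 1.22 − ln 0.68)/3.92 = 0.1491. An analysis of 201 events at 2:1 would give 1/√(201 × 2/9) = 0.1496, so the published interval fits the 201-event analysis. Against 1.3, z = (ln 1.3 − ln 0.91)/0.1491 = 2.392, two-sided p = 0.017. The 99.9% upper bound is 0.91 × exp(3.2905 × 0.1491) = 1.49, above 1.3, which agrees with the reported failure. The 95% bound, 1.22, would have passed.

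**3. Total error if both tests form one family.** The upper limit is 0.001 + 0.05 = 0.051. With independent tests it is 1 − 0.999 × 0.95 = 0.05095. With overlapping data, take the correlation as shared events/√(201 × 688) and compute the bivariate normal union:

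| Shared events | Correlation | Two-sided total | Relevant tail, 0.001 two-sided | Relevant tail, 0.001 one-sided |
|---|---|---|---|---|
| 0 | 0 | 0.05095 | 0.02549 | 0.02597 |
| 100 | 0.269 | 0.05085 | 0.02543 | 0.02586 |
| 201 | 0.541 | 0.05052 | 0.02526 | 0.02557 |

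Only one tail can wrongly exclude 1.3. Its nominal level is 0.025, so the excess is 0.0003 to 0.0005 if the 0.001 was two-sided and 0.0006 to 0.0010 if one-sided. The true correlation is unknown because endpoint and study pool differ.

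**4. Effect of a final level of 0.049.**

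- Power at 688 events, 2:1: 90.05% becomes 89.89%. With mixed allocation, 91.4% becomes 91.3%.
- Events for 90% power at 2:1: 687 becomes 691.
- Largest HR that still passes, 1.3 × exp(−z/12.365): 1.1094 becomes 1.1087.

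At exactly 688 events, the two rules disagree only if the final HR lands in an interval 0.0007 wide.

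**The case for a change.** The strongest case for a change is that section 11.8.2 prints both levels side by side, attaches them to the same condition, and leaves a total that does not come to 0.05. The early level also decided the outcome, since p = 0.017 passes at 0.05 and fails at 0.001. The remedy is cheap, and differences in endpoint or study pool alter the correlation but not the 0.051 bound.

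Part of this stands. The label in 11.8.2 and the wording in 1.2 do support reading the tests as one condition, the data overlap, and the sidedness of the 0.001 is not given.

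The rest does not carry a change:

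- **Different hypotheses.** The first test concerned MACE plus hospitalized unstable angina across the Phase 3 program, against active or placebo control (section 11.8.1). The final one concerns MACE alone, in two placebo-controlled studies, under a requirement that FDA restated at approval. The INT-6 amendment summary records, as history, that the formerly planned 500- and 700-event analyses were dropped in favour of this one, so the 0.001 may belong to an abandoned sequence.
- **No broken promise.** The 5% family-wise statement in section 11.5.3 covers MACE superiority and then the albuminuria and HOMA-B endpoints within CANVAS. It does not extend to successive meta-analyses.
- **The p-value of 0.017 shows no inflation.** It shows that the strict early threshold was applied and respected.
- **The remedy has drawbacks.** A 95.1% decision rule would sit beside FDA's 95% criterion in the same section and might conflict with an SAP already submitted. The figure 0.049 also presumes a two-sided 0.001; no final level follows if it was one-sided.

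**Conclusion.** The concern is arithmetically correct but conditional, and nothing in the plan needs to change. Overall error exceeds the nominal level only if the two meta-analyses are treated as one error family. Even then the two-sided total is at most 0.051 with a two-sided 0.001, and the relevant tail is at most 0.0255 (0.0260 if the 0.001 was one-sided) against 0.025. Leaving the final level at 0.05 after a look at 0.001 is the familiar Haybittle-Peto pattern, accepted because the inflation is negligible. The deduction would cost about 0.16 points of power at 2:1 and change almost no conceivable decision, while adding a second confidence level next to the regulatory one.

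What remains is missing detail: the sidedness of the 0.001 and how alpha is accounted for across the meta-analyses. That belongs in the separate meta-analysis SAP, and its absence from the protocol is not an error. The 95% CI criterion, the 688-event target and the power of about 90% all stand. The power figures assume a true HR of 1.0 and 2:1 allocation throughout.

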11.9. Glycemic Efficacy Substudies

11.9.1. Analysis Sets

The mITT analysis set includes all subjects who are randomly assigned to a treatment group and received at least one dose of study medication. The per-protocol (PP) analysis set will consist of all mITT subjects who completed 18 weeks of treatment, and have no protocol deviations that may affect the interpretation of the primary efficacy endpoint (to be defined in the SAP before database lock and unblinding of the treatment groups) and have not received glycemic rescue therapy. The primary efficacy analysis will be based on the mITT set. The efficacy data measured after the initiation of rescue therapy will be treated as missing. Analysis based on the PP set will also be conducted as a sensitivity analysis.

Efficacy data will be analyzed according to the randomization assignment, regardless of actual treatment received. Safety data will be analyzed according to actual treatment received. The approaches to handle study treatment deviations will be detailed in the SAP.

11.9.2. Sample Size Determination

The primary objectives of the substudies are to compare the HbA_{1c}-lowering efficacy of canagliflozin with placebo after 18 weeks of treatment, in subjects on specific AHAs.

With the exception of the sulfonylurea substudy, assuming a group difference of 0.50% and a common SD of 1.0% with respect to change in HbA_{1c}, and using a 2-sample, 2-sided t-test with Type I error rate of 0.05, it is estimated that 258 randomized subjects (86 subjects in each of the 3 treatment groups) would provide 90% power.

Recently published literature with another SGLT2 inhibitor (Strojek 2010) suggest that the observed standard deviation with respect to HbA_{1c} change from baseline in subjects taking sulfonylureas is less than originally anticipated in the protocol (ie, SD was reported to be 0.75% instead of 1.0%). These new data would allow for an assessment of the primary substudy endpoint (ie, change in HbA_{1c} from baseline) in the sulfonylurea substudy using a smaller sample size in this substudy, ie, 150 randomized subjects (50 subjects in each of the 3 treatment groups) would provide 90% power.

11.9.3. Efficacy Analyses

For each substudy, except the sulfonylurea substudy as noted above, the primary efficacy analysis will only be performed when sufficient subjects (≥ 258) in the subpopulation are

randomized in each of the 3 treatment groups (≥ 86 per group). The analysis will be conducted when the sponsor prepares for the regulatory submissions. For the sulfonylurea substudy, the primary efficacy analysis will only be performed when sufficient subjects (≥ 150) in the subpopulation are randomized in each of the 3 treatment groups (≥ 50 per group).

[figure not shown]
The primary efficacy endpoint will be the change in HbA_{1c} from baseline through Week 18. The LOCF method will be applied when the Week 18 values are missing. In subjects receiving rescue therapy, their measurements made before rescue will be used as the last observation. An ANCOVA model with treatment as a fixed effect and the corresponding baseline value as covariate will be used. The treatment difference (each dose of canagliflozin minus placebo) in the least-squares means and the 2-sided 95% CI will be estimated based on this model.

As a supportive analysis, change from baseline in HbA_{1c} will be analyzed using a restricted maximum likelihood (REML) based on repeated measures approach. The analysis will be based on observed data and will include the fixed, categorical effects of treatment, visit, and treatment-by-visit interaction, as well as the continuous, fixed covariates of baseline and baseline-by-visit interaction. An unstructured covariance will be used to model the within-subject errors. The treatment comparisons will be made between each dose of canagliflozin and placebo at Week 18 and significance tests will be based on the difference of the least-squares means.

The secondary efficacy evaluations of change in body weight, FPG, and systolic and diastolic blood pressure, and percent change in fasting plasma lipids will be analyzed using an ANCOVA model similar to that used in the primary efficacy analysis. The percentage of subjects with HbA_{1c} $< 7\%$ at Week 18 will be assessed by means of a logistic model with treatment and stratification factors as fixed effects and baseline HbA_{1c} as a covariate.

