The effects of different baseline demographic variables (eg, age, race, sex) as well as other important baseline disease characteristics (eg, history of prior CV disease, key concomitant therapy use, and region) on the primary endpoint will be explored; a detailed discussion of subgroup analyses will be provided in a SAP for this study which will be finalized before the first interim analysis.

Major Secondary Efficacy Analysis

Changes from baseline in the continuous variables of HOMA-B and the proinsulin/insulin ratio, HbA_{1c}, FPG, blood pressure, body weight, albuminuria, and eGFR, and percent change in fasting lipids will be analyzed using an analysis of covariance (ANCOVA) model with treatment (canagliflozin 100 mg, canagliflozin 300 mg, or placebo), and stratification factors as a fixed effect and the corresponding baseline value as a covariate. The treatment difference (each dose of canagliflozin minus placebo) in the least-squares means and the 2-sided 95% CI will be estimated based on this model. The analyses for beta-cell function will be conducted on subjects not receiving insulin at randomization and, for subjects who are started on insulin during the study, the last data point before the initiation of insulin will be included for these analyses.

The categorical secondary efficacy endpoint is the proportion of subjects with progression of albuminuria (defined as ≥ 1 step increase, ie, no albuminuria to micro- or macro-albuminuria or from micro-albuminuria to macro-albuminuria). The proportion of subjects with progression of albuminuria will be analyzed using

the logistic model with treatment (canagliflozin 100 mg, canagliflozin 300 mg or placebo) and stratification factors as a fixed effect.

Multiplicity Adjustment

To ensure the family-wise Type I error rate (alpha level) in this study is at most 5%, a gatekeeping procedure will be applied in testing the primary and secondary hypotheses.

Interim Analysis

Interim analyses of CANVAS will be done to prepare: (1) an interim safety report in support of the initial health authority filing, (2) the 18-week substudy reports, and (3) the CV safety meta-analyses (based on adjudicated data). The interim data from the CANVAS study will primarily supplement the safety and tolerability data generated from other studies in the canagliflozin development program.

TIME AND EVENTS SCHEDULE (CONTINUED)

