5. TREATMENT ALLOCATION

To ensure sufficient experience in subjects with documented, pre-existing CV disease—the highest risk group—approximately 70% (minimum of 60%) of subjects (globally) are targeted to be in this group.

Stratification for Substudies

Subjects will have within-subgroup balanced (1:1:1) randomization to each of the 3 treatment groups within the following 6 predefined strata, which are based upon AHA medication(s) that the subject is receiving at the run-in visit and will be continuing at entry into the double-blind treatment phase:

- Stratum 1: insulin monotherapy ≥ 20 units per day, on stable doses at least 10 weeks before the run-in visit
- Stratum 2: insulin ≥ 20 units per day plus metformin, on stable doses at least 10 weeks before the run-in visit, and no other background AHA therapy
- Stratum 3: insulin ≥ 20 units per day plus any other AHA(s) on stable dose(s) for at least 10 weeks before the run-in visit
- Stratum 4: sulfonylurea monotherapy (at doses specified in [Attachment 1](#)), on stable doses at least 10 weeks before the run-in visit
- Stratum 5: pioglitazone ≥ 30 mg/day plus metformin $\geq 2,000$ mg/day (or at least 1,500 mg/day for subjects who have a history of not being able to tolerate higher metformin doses) and no other background AHA therapy, on stable doses at least 10 weeks before the run-in visit
- Stratum 6: subjects not in one of the above AHA subgroups

Note: a stable dose of insulin is defined as no change in the insulin regimen (ie, type[s] of insulin) and $\leq 15\%$ change in the average total daily dose of insulin (as averaged over one week).

The stratification process will be handled via queries in the Interactive Voice Response System (IVRS) or after logging on to the Interactive Web Response System (IWRS) being used for the study, described below.

Randomization and Blinding Procedures

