11.5.2. Major Secondary Efficacy Endpoints

The continuous secondary efficacy endpoint, change from baseline in HOMA-B will be analyzed using an analysis of covariance (ANCOVA) model with treatment (canagliflozin 100 mg, canagliflozin 300 mg or placebo) and stratification factors as fixed effects and the corresponding baseline value as a covariate. The treatment difference (each dose of canagliflozin minus placebo) in the least-squares means and the 2-sided 95% CI will be estimated based on this model. The analyses for beta-cell function will be conducted on subjects not receiving insulin at randomization and, for subjects who are started on insulin during the study, the last data point before the initiation of insulin will be included for these analyses.

The categorical secondary efficacy endpoint is the proportion of subjects with progression of albuminuria (defined as ≥ 1 step increase, ie, no albuminuria to micro- or macro-albuminuria or from micro-albuminuria to macro-albuminuria). The proportion of subjects with progression of albuminuria will be analyzed using the logistic model with treatment (canagliflozin 100 mg, canagliflozin 300 mg or placebo), and stratification factors as a fixed effect. Albuminuria will be assessed according to the categorizations defined in the National Kidney Foundation Kidney Disease Outcomes Quality Initiative Guideline #1 (KDOQI 2007): the definition of micro-albuminuria is albumin/creatinine ratio of 30 to 300 mg/g, and the definition of macro-albuminuria is albumin/creatinine ratio greater than 300 mg/g.

For the secondary endpoints of HOMA-B and proportion of subjects with progression of albuminuria, the analyses will compare the dose groups, *combined* and *individually*, relative to placebo.

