11.5.4. Additional Secondary Efficacy Endpoints

Additional efficacy endpoints of interest will include the following:

- changes from baseline to end-of-treatment in the proinsulin/insulin ratio (in a subset of subjects), urinary albumin/creatinine ratio, and eGFR
- changes from baseline to Week 18 in HbA_{1c}, FPG, systolic and diastolic blood pressure, and body weight
- percent change from baseline to Week 18 in fasting plasma lipids (triglycerides, HDL-C, LDL-C, total cholesterol, and the ratio of LDL-C to HDL-C)

The continuous secondary efficacy endpoints, changes from baseline in the proinsulin/insulin ratio, HbA_{1c}, FPG, body weight, blood pressure, albuminuria, and eGFR and percent change in fasting lipids will be analyzed in the same manner as the secondary efficacy endpoint, change from baseline in HOMA-B.

For the assessment of change from baseline in HbA_{1c} at Week 18, subgroup analyses (described in detail in the SAP for this study) will be conducted to enhance understanding of factors that might impact glycemic response to canagliflozin.

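### The insulin substudy's HbA1c models leave out the randomisation strata that its responder model includes (minor; a free improvement)

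*Protocol*

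**What the plan says.** Section 5 of the protocol, under the heading "Stratification for Substudies", sets up 1:1:1 allocation within six strata of background antihyperglycemic therapy, using permuted blocks. Strata 1 to 3 are insulin of at least 20 units/day: alone, with metformin only, and with any other agent(s). Stratum 4 is sulfonylurea monotherapy and stratum 5 is pioglitazone plus metformin. Section 3.1 defines the insulin substudy as insulin of at least 20 units/day with or without other agents, so it is made up of strata 1 to 3.

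Section 11.9.3 then gives these substudy models:

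- Primary, change in HbA1c at Week 18: "An ANCOVA model with treatment as a fixed effect and the corresponding baseline value as covariate will be used".
- Supportive repeated measures: it "will include the fixed, categorical effects of treatment, visit, and treatment-by-visit interaction", plus baseline and baseline-by-visit. No strata.
- Continuous secondary endpoints: "using an ANCOVA model similar to that used in the primary efficacy analysis".
- HbA1c <7%: a "logistic model with treatment and stratification factors as fixed effects", with baseline HbA1c as covariate.

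In the main study, Section 11.5.4 says that the continuous endpoints, Week 18 HbA1c among them, "will be analyzed in the same manner as the secondary efficacy endpoint, change from baseline in HOMA-B". That model, in Section 11.5.2, has treatment and "stratification factors as fixed effects and the corresponding baseline value as a covariate". The Synopsis names HbA1c directly and also lists "stratification factors as a fixed effect and the corresponding baseline value as a covariate".

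**The concern.** Stratified blocks balance the arms on background therapy, so differences between strata no longer contribute to the error of the treatment contrast. A model without the strata still counts those differences as residual variance. If the strata predict change in HbA1c after adjustment for baseline, the reported standard error is larger than the true one, the test is conservative and the interval is too wide.

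The text is also inconsistent. Within Section 11.9.3 the responder analysis adjusts for strata and the primary analysis of the same measurement does not. Change in HbA1c at Week 18 is adjusted in the main study and not in the substudy. No reason is given for either difference. The insulin substudy is the only one in which the responder model's stratification term can have more than one level, and so the only one in which the mismatch has any effect.

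**Working it through.** **Inputs from the protocol (Section 11.9.2).** Difference 0.50%, SD 1.0%, two-sided alpha 0.05, 86 per group, 90% power.

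**Input assumed.** R², the share of residual variance explained by the three insulin strata given baseline HbA1c. The protocol gives no value, so I use 0, 2, 5 and 10%. I also treat the SD of 1.0% as the residual SD after baseline adjustment.

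**The plan's own figure.** Normal formula: n = 2(1.960 + 1.282)² × 1.0² / 0.50² = 84.1, so 85 per group. The exact t-test gives 85.03, so 86, with 90.3% power at 86. The stated sample size reproduces.

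**Effect of omitting the strata (normal approximation).**

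- Standard error reported without strata: √(2/86) × 1.0 = 0.1525. CI half-width: 1.96 × 0.1525 = 0.299.
- True standard error with allocation balanced in strata: 0.1525 × √(1 − R²).
- Excess CI width: 1/√(1 − R²) − 1.
- True alpha without strata: 2[1 − Φ(1.96/√(1 − R²))].
- Power without strata: Φ[(0.50 − 0.299)/(0.1525√(1 − R²))].
- Power with strata: Φ[0.50/(0.1525√(1 − R²)) − 1.96].
- Spread in mean change between the extreme strata needed for that R², with three equal, evenly spaced strata: 2√(1.5R²) × 1.0.

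| R² | True alpha without strata | CI half-width without / with | CI excess | Power without / with | Spread needed (percentage points) |
|---|---|---|---|---|---|
| 0% | 0.050 | 0.299 / 0.299 | 0% | 90.6% / 90.6% | 0 |
| 2% | 0.048 | 0.299 / 0.296 | 1.0% | 90.9% / 91.2% | 0.35 |
| 5% | 0.044 | 0.299 / 0.291 | 2.6% | 91.2% / 92.0% | 0.55 |
| 10% | 0.039 | 0.299 / 0.284 | 5.4% | 91.8% / 93.3% | 0.77 |

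**Cost if the strata are not prognostic.** Two residual degrees of freedom. Noncentral-t power is 90.428% with 254 df and 90.426% with 252 df.

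**Simulation check.** I used 20,000 three-arm trials per scenario, 258 subjects, and ANCOVA with baseline, without and then with the stratum. With permuted blocks of 6 (an assumed size), for R² of 0, 2, 5 and 10%:

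- Type I error without/with: 0.0483/0.0482, 0.0489/0.0506, 0.0430/0.0491, 0.0391/0.0488.
- Power without/with: 90.6/90.5%, 90.9/91.2%, 90.9/91.7%, 91.6/93.0%.
- Mean estimate: −0.500 to −0.501 under both models, so no bias.

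A second simulation with exact balance within strata gave type I error without strata of 0.0485, 0.0495, 0.0452 and 0.0408, and power gains of 0 to about 2 points. The Monte Carlo standard error is about 0.0015 for alpha and 0.002 for power, so at R² = 2% the shortfall in alpha cannot be told apart from noise.

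**The case against.** The strongest reply is that nothing the plan promises fails. Treatment plus baseline is a valid, slightly conservative model, and power stays above 90%. It is written once for three substudies, two of which have a single stratum where the term cannot be estimated. Section 11 describes itself as general and leaves specifics to the SAP, which was not available here. Section 2.3 keeps the substudy hypotheses separate from the main study, so different models could be defended.

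Most of this limits the weight of the point without removing it. The validity argument is accepted in full. Deferral to the SAP does not settle the matter, because Section 11.9.3 lists the terms of each model and lists them differently. The continuous secondary models are a softer case, since they are only described as similar to the primary one. The comparison with the main study is weaker than the mismatch inside Section 11.9.3.

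The size does rest on assumption. Spreads of 0.55 and 0.77 points between strata exceed the 0.50 design effect, so 5% and 10% are generous values. If baseline HbA1c reduces the residual SD below 1.0%, the half-widths shrink in absolute terms. The 86 per group is also a minimum, so a larger substudy would lose less power.

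Timing is the most practical objection. Section 11.9.3 ties the analysis to regulatory submissions, the Introduction records US approval in March 2013, and the current amendment is dated May 2016. The substudy has very probably been reported, and replacing its primary model now would be post hoc.

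**Conclusion.** The concern holds as a minor point, confined to the insulin substudy. The primary ANCOVA and the repeated-measures model omit strata that were balanced by design and that the responder model in the same section includes; the continuous secondary models follow by reference. The treatment estimate is unbiased, type I error is not inflated and the planned sample size stands. What is given up is some precision: nothing if the strata are not prognostic, about 1% of CI width and 0.3 points of power at an R² of 2%, and 5.4% of width and 1.5 points at 10%, which I regard as an upper bound. These figures are illustrative because R² is assumed. The primary MACE Cox model in Section 11.5.1 is not part of this point.

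**What to change.** If the insulin substudy has not been reported, add one clause to Section 11.9.3: the three-level insulin stratum (strata 1, 2 and 3 as recorded in IVRS/IWRS) enters as a fixed effect in that substudy's primary ANCOVA, continuous secondary ANCOVAs and repeated-measures model. State that the sulfonylurea and pioglitazone-metformin substudies need no such term, since each is a single stratum; this also clarifies what the responder model's stratification factors mean there.

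If it has been reported, which is likely, leave the reported model as primary and add the stratum-adjusted model as a labelled sensitivity analysis.

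The strata are already held from randomisation, so no new data are needed. The cost is one clause or one extra table, and under 0.01 point of power if the strata turn out not to matter.
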